3. OBJECTIVE AND OUTCOME MEASURES/ ENDPOINTS

Primary objectives

The primary objectives are twofold:

- a. To understand the distribution of LUTS score in patients undergoing renal transplantation
- b. To describe the distribution of LUTS scores across adverse outcomes post-transplant

Secondary objectives

- Evidence of urological complications in the 6 weeks following transplantation.
- Evaluation of whether the presence of LUTS can predict graft outcomes in the 12 months following transplantation
- Whether or not pre-existing urological conditions increase the likelihood of major urological complication following transplant
- Compare patients undergoing this work-up regimen with an age/ sex matched historical cohort to determine if there is any difference in risk of post-operative urological complications with a focused pre-operative screening regimen.
- Determination of whether changing the peri-operative work-up pathway to evaluate pre-operative LUTS, will reduce the likelihood of urological complications in the year following transplant
- To assess the change in LUTS and QOL by validated tools at 6 weeks and 1 year post RT after re-establishment of diuresis.
- To assess whether duration of time on the waiting list/ presence of anuria impacts on primary outcomes and change in severity of LUTS/ QoL. Inform future end points, sample size, trial design etc. of a future interventional study
- Determination if the duration of time on the transplant waiting-list and/ or RRT vintage and/or anuria predict objective change in LUTS or adverse urological outcomes post-transplant

Primary outcome measures

LUTS will primarily be assessed using IPSS for male participants and ICIQ-FLUTS for female participants (see below), supplemented by post-void residual volume and urine flow studies.

“Urological complication” will be considered to be a composite any of the following occurring within the first 12 months following transplantation:

1. Urinary retention defined as high post-void residual volumes initiating need for indwelling catheter/ clean intermittent catheterization within the first 12 months of transplantation. (This will include patients who fail trial of void post-surgery).
2. Recurrent culture-proven urinary tract infections (≥ 2 in the first 6 months/ ≥ 3 in the first 12 months post-transplant)
3. Ureteric leak or suspected ureteric leak.
4. Deterioration in renal function (eGFR, Creatinine) due to post-renal causes:

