All patients have the right to refuse participation without giving reasons. Participants remain free to withdraw from the trial at any time without giving reasons and without prejudicing his/her further treatment. If a patient declines to consent a record of this will be made within the patient notes and in the SCOPE study screening log.

Once signed, a copy of the consent form will be given to the patient; the original kept in the local ISF and a copy placed in the patient notes. The informed consent discussion will be recorded in the participant's medical notes including the version number of the PIS provided to the participant.

Patients recruited into the trial will be assigned a unique patient identifier allowing participant to be identified i.e. 001 on all future trial documentation. An enrolment log will be maintained in the ISF to permit identification of patient names against trial numbers for those recruited to the trial. The ISF will be retained at a secure location within the Renal Transplant Unit. The enrolment log is the only place where patient identifiable information will be recorded. Upkeep and security of the ISF is the responsibility of the PI.

Interventions/ trial procedures

The interventions within this study beyond standard care are the bladder diary, IPSS/ ICIQ-FLUTS questionnaire, a bladder scan (bedside ultrasound) to measure post-void residual volume and non-invasive uroflowmetry studies. These additional interventions will be performed at time of transplant listing (where appropriate), after 1 year on the transplant waiting list (where appropriate), on the day of transplant, 6 weeks and 12 months after transplantation.

A small number of patients will not pass sufficient urine to perform flow studies/ and or urodynamics. These patients will require their bladder to be pre-filled with sterile saline prior to voiding in order to achieve an accurate reading. A protocol for how to undertake this is outlined in Appendix 1 and would be performed by the ward doctor as part of clinical care. The rates of bladder filling and urodynamic studies being performed within trial will be monitored by the Trial Steering Committee at 3- 6 monthly intervals to ensure that these are clinically appropriate.

Study visits

A schedule of study visits is outlined below. All study visits will correspond to pre-existing clinical visits.

For patients recruited on day of transplant:

Study assessments	Visits			

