	Screening visit	Enrollment visit (Day of transplant or day -1)	Week 6 +/- 2 weeks	Week 52 +/- 4 weeks
Assessment against eligibility criteria	X			
Provision of PIS	X			
Informed consent		X		
Demographics and past medical/urological history		X		
Bladder diary		X	X	X
IPSS/ICIQ		X	X	X
Bladder diary		X	X	X
Renal function		X	X	X
Uroflowmetry ⁺		X	X	X
Post-void residual ⁺		X	X	X
Urodynamics ⁺⁺		(X)	(X)	(X)
Urological complications			X	X
Other secondary outcome measures			X	X

For patients recruited in the transplant assessment clinic:

Study assessments	Visits					
	Screening visit	Enrollment visit (Transplant assessment)	1-year post-waiting listing*	Day of transplant or day -1)	Week 6 +/- 2 weeks	Week 52 +/- 4 weeks
Assessment against eligibility criteria	X					
Provision of PIS	X					
Informed consent		X		X		
Demographics and past medical/urological history		X	X	X		
Bladder diary		X	X	X	X	X
IPSS/ICIQ		X	X	X	X	X
Bladder diary		X	X	X	X	X
Renal function		X	X	X	X	X
Uroflowmetry*		X	X	X	X	X
Post-void residual*		X	X	X	X	X
Urological complications					X	X
Other secondary outcome measures					X	X

Data collection

Data will be collected from standardized data collection tools as outlined in section 7 and from within the Scottish Renal Electronic Record (SERPR).

Demographics, past medical and surgical history

Patient factors: Age, Gender, Ethnicity, BMI, Postcode

Relevant past medical history: Diabetes, Hypertension, Ischemic heart disease, cause of primary renal disease; RRT vintage; prior transplantation and duration of same; reason for prior graft loss if previous transplant

Past and present urological history: Any prior urological diagnosis/ interventions/ surgery; native urinary output; any prior urological assessment of bladder function/ volumes; LUTS symptoms (storage- frequency, urgency, nocturia, voiding- dribbling, struggling to initiate, incomplete emptying), caffeine and fluid intake, previous/ current use of catheters, previous urological surgeries, use of medications for LUTS (anticholinergics, 5-alfa reductase inhibitors, alfa agonists, intravesical Botulinum Toxin-A)

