8 STATISTICS AND DATA ANALYSIS

Sample size

This is a non-interventional, exploratory study, the results of which we hope will may inform a future interventional study. The primary aims are two-fold:

- a. To understand the distribution of LUTS score in patients undergoing renal transplantation
- b. To describe the distribution of LUTS scores across adverse outcomes post-transplant

Our sample size has been chosen based on three factors:

1. Feasibility within the anticipated timescale
2. The likelihood of obtaining a representative distribution of LUTS scores assuming a relatively normal distribution from other feasibility studies
3. The existing literature (it'll be the largest observational study of evaluating LUTS in transplant patients, and the only one to evaluate longitudinally)

We aim to recruit 100 patients into each of the two parts of the study over two years.

The Glasgow Renal Transplant Unit performs 100-150 renal transplants annually and assesses over 200 patients per year. Conservatively, over a two year period, 100 patients could be recruited by approaching and consenting less than half of those transplanted and fewer than 25% of those assessed for transplantation.

We anticipate a 5-10% death rate (as would be standard in the transplant population). We do not anticipate that patients will be lost to follow-up as they all come back to regular post-transplant clinics, but assuming 5-10% withdraw or have incomplete data sets that should still leave a minimum of 40 men and 40 women with complete datasets for evaluation.

There is little data on the prevalence or distribution of LUTS in the renal transplant population in men¹⁵⁻¹⁷, and no data in women. Based on the previous two year's data from our own center we anticipate that between 50-60% of patients will have one of the composite urological complication outcomes. (We have deliberately chosen a broad definition of "urological complications", with high prevalence, for this initial study so that

all possible relevant outcomes are considered so that all relevant outcomes are considered and recorded. This could be refined for future interventional studies to be more specific if deemed appropriate.)

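### Residual scans scheduled by the study can lead to retention events that usual care might not have detected, which exposes the historical comparison to unequal ascertainment

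*Protocol*

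**What the plan says.** Section 3, Primary outcome measures, item 1 defines the component as "Urinary retention defined as high post-void residual volumes initiating need for indwelling catheter/ clean intermittent catheterization" and limits it to 12 months after transplant. It adds that "This will include patients who fail trial of void post-surgery". The Scientific Summary carries the same item. Neither place gives a residual volume or says what must have prompted the measurement.

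Section 7, Interventions/trial procedures, lists what the study adds to standard care. The list includes "a bladder scan (bedside ultrasound) to measure post-void residual volume and non-invasive uroflowmetry studies", to be done, among other times, "on the day of transplant, 6 weeks and 12 months after transplantation". Both visit schedules in Section 7 mark the residual for every patient at week 6 and at "Week 52 +/- 4 weeks".

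Two other places point the other way. Section 7, Post-void residual bladder volume, describes the scan as routine. Section 9, Assessment and management of risk, expects no tests beyond standard care.

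Section 8, Sample size, says of the unit's previous two years of data that "we anticipate that between 50-60% of patients will have one of the composite urological complication outcomes". Section 8, Data analysis, makes the prevalence of urological complications a primary aim, meant to inform a later trial. Section 3 also plans a comparison of complication risk with a historical cohort matched on age and sex.

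**The concern.** Whether this component is recorded depends partly on whether anyone measures a residual. The study measures it in every patient at two fixed follow-up visits, and Section 7 says this is extra. If a patient without complaints is found to have a high residual at week 6 and a catheter follows, that patient has a composite event. Under earlier care the same patient might never have been counted.

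Nothing in the protocol separates the two routes. It does not withhold the result from the treating team, record the reason for catheterisation or adjudicate the event. Appendix 1 deals with equivocal tests on the day of transplant and in pre-assessment clinic, not at follow-up.

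Two results are exposed. The historical comparison would set a cohort scanned on schedule against one that, on Section 7's wording, was not. That bias works against the new work-up. The prevalence estimate offered for planning a later trial could also sit somewhat above the rate under usual care. If the trigger is not recorded when the event occurs, it will be hard to reconstruct.

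**Working it through.** **The plan's own figures.** Section 8 expects at least 40 men and 40 women with complete data out of 100. With the upper loss rates this reproduces: 100 × (1 − 0.10 − 0.10) = 80, or 100 × 0.90 × 0.90 = 81, which is 40 to 40.5 per sex at an even split. The 50-60% composite rate comes from the unit's own data and cannot be re-derived from the document.

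**Effect on the composite.** Let p be the composite rate without scan-found events and x the share of otherwise event-free patients catheterised only because of a study scan. Then observed rate = p + (1 − p) × x. Here p is 50-60% from Section 8. The documents give no x, so 2%, 5% and 10% are assumptions.

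| p | x = 2% | x = 5% | x = 10% |
|---|---|---|---|
| 50% | 51.0% | 52.5% | 55.0% |
| 55% | 55.9% | 57.3% | 59.5% |
| 60% | 60.8% | 62.0% | 64.0% |

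The smallest rise is 0.40 × 0.02 = 0.8 points and the largest is 0.50 × 0.10 = 5 points, so about 1 to 5 extra events per 100 patients. Patients with a high residual may also tend to have infections or post-renal decline. In that case the share among the event-free, which is the x that counts, is smaller than the share among all patients.

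**Against sampling error.** The 95% half-width at n = 100 is 1.96 × √(p(1 − p)/100): 9.8 points at p = 50% and 9.6 at p = 60%. The shift is smaller than this, but a larger sample would not remove it.

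**Effect on the historical comparison.** The protocol gives neither the size of the historical cohort nor an expected difference. As an illustration, assume 55% in the historical cohort, a true 45% in the study and 100 per group. The observed study rate is 0.45 + 0.55x. Power is for a two-sided 5% test of two proportions, normal approximation, treating the groups as independent.

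| x | Observed study rate | Apparent reduction | Power |
|---|---|---|---|
| 0 | 45.0% | 10.0 points | 29% |
| 2% | 46.1% | 8.9 points | 24% |
| 5% | 47.75% | 7.25 points | 17% |
| 10% | 50.5% | 4.5 points | 9% |

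Power is low even without the bias. The point is that scan-found events alone could hide up to about half of a real 10-point reduction.

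**Timing.** Item 1 stops at 12 months and the last visit may fall up to week 56, so a catheter started after a scan in weeks 53 to 56 does not count. Most of any effect would come from the 6-week scan. Retention shown by a failed trial of void is not affected.

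**The case against.** The strongest reply is that a scan is never an event. A catheter must follow, and no text links a follow-up study scan to catheterisation. That stands: the documents support saying that scans can lead to events. A reader might infer that the scans themselves create them, and the text does not support that.

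Nor is it settled that the scans are purely for the study, given the two places that treat them as usual care. Section 7's list is the more specific statement, but how many such scans the earlier patients had is unknown.

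Section 8 deliberately chooses a broad composite, to be refined later, and Section 3 plans to report complications by type. This is a fair reason to keep the composite as it is. It concerns which outcomes count, though, not how they come to be detected.

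Some patients found by the 6-week scan might have presented clinically within the year. Dropping them could understate the usual-care rate, so the version without them is not that rate either. This stands and is why both versions are needed.

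Everyone in the study follows the same scan schedule, so the comparison of LUTS scores across outcomes within the cohort is less affected. The sample size rests on feasibility, the expected LUTS distribution and existing literature, not on the 50-60% figure. A reader might infer that the sample size is undermined, and it is not.

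Finally, the same finding could count at week 50 and not at week 54. A reader might take this for a fault, but it is the ordinary edge of any fixed 12-month horizon.

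**Conclusion.** The concern holds as an ascertainment problem of modest and unknown size. On Section 7's wording, scheduled scans can add retention events that the earlier data would not have contained. The historical comparison is the most exposed, in the direction unfavourable to the new work-up. The prevalence estimate may be raised by about 0.8 to 5 points. That range rests on an assumed 2-10% of otherwise event-free patients catheterised only because of a study scan, and on earlier patients not having had equivalent scans.

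A reader might go further and conclude that the primary composite should be restricted to clinically prompted retention. The documents do not support that step. The breadth is declared and explained, and the narrower version is not itself the usual-care rate. Nor do they support any firm estimate of how many scan-found events there will be.

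**What to change.** - Keep the broad composite as primary.
- For each retention event, add one field recording whether it was prompted by symptoms, a failed trial of void or other clinical care, or was first found on a scheduled study scan.
- Report the composite with and without scan-found events. A patient dropped on this component still counts if another component is met.
- Use the version without scan-found events in the historical comparison. State that some of these cases might have presented later, so the two versions bracket the usual-care rate, provided that catheterisation after a scan does not itself bring about another component.
- Reconcile Section 7, Interventions/trial procedures, with Section 7, Post-void residual bladder volume, and Section 9, Assessment and management of risk, on whether the scan is standard care.

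The cost is one data field and one extra analysis. Classification will be imperfect, because symptoms, flow and residual are collected at the same visit. Patient care does not change.

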1. Urinary retention defined as high post-void residual volumes initiating need for indwelling catheter (IDC)/ clean intermittent catheterization (CISC) within the first 12 months of transplantation. (This will include patients who fail trial of void post-surgery).
2. Recurrent culture-proven urinary tract infections (≥ 3 in the first 12 months post-transplant)
3. Ureteric leak or suspected ureteric leak requiring surgical or radiological intervention
4. Deterioration in renal function (eGFR, Creatinine) due to post-renal causes:
 - Transient decline in renal function ($>20\%$ from nadir creatinine)
 - Persistent decline in renal function ($>10\%$ from nadir creatinine)
5. Sepsis of urinary source requiring hospital admission (including graft pyelonephritis)
6. Any patient undergoing any surgical or radiological intervention for a urological complication (excluding routine stent removal post-transplant) within the first 12 months of transplantation
7. Graft loss as a result to urological complications within the first year of transplantation

Secondary outcomes will include:

1. Evidence of urological complications in the 6 weeks following transplantation.
2. Evaluation of whether the presence of moderate-severe LUTS can predict graft outcomes in the 12 months following transplantation
3. Determination if the duration of time on the transplant waiting-list and/ or RRT vintage and/or anuria predict objective change in LUTS or adverse urological outcomes post-transplant

4. Whether or not pre-existing urological conditions increase the likelihood of major urological complication following transplant
5. Compare patients undergoing this work-up regimen with an age/ sex matched historical cohort to determine if there is any difference in risk of post-operative urological complications with a focused pre-operative screening regimen.
6. Determination of whether changing the peri-operative work-up pathway to evaluate pre-operative LUTS, will reduce the likelihood of urological complications in the year following transplant

Timeline for delivery:

Recruitment will commence in January 2026 and is anticipated to continue for 2 years. Follow-up will cease when all patients recruited are > 1 year post-transplant; have been removed from the transplant waiting-list or will have died.

Anticipated impact and dissemination:

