 - Transient decline in renal function ($>20\%$ from nadir creatinine)
 - Persistent decline in renal function ($>10\%$ from nadir creatinine)
5. Sepsis of urinary source requiring hospital admission (including graft pyelonephritis)
6. Any patient undergoing any surgical or radiological intervention for a urological complication (excluding routine stent removal post-transplant) within the first 12 months of transplantation
7. Graft loss as a result to urological complications within the first year of transplantation

Secondary outcome measures

- Renal function at 12 months (eGFR, creatinine) and its association with presence and severity of pre-transplant LUTS
- Change in IPSS/ ICIQ-FLUTS scoring from baseline to 6 weeks and 1 year post RT (including QoL scores)

Table of endpoints/ outcomes

Objectives	Outcome Measures	Timepoints
Primary Objective:		
To determine the prevalence of distribution of pre-transplant LUTS	LUTS at baseline as assessed by IPSS/ ICIQ-FLUTS, flow studies and post-void residual urine volumes	Baseline
To determine the distribution of LUTS scores across adverse urological complications post-transplant	Incidence of urological complications (retention, recurrent UTIs, ureteric obstruction, need for CIC, graft pyelonephritis etc as above)	6 weeks and 12 months post-transplant
Secondary Objectives:		
To assess change in LUTS over time (includes QoL)	IPSS/ ICIQ total score and QoL sub-score, post-void residual volumes, Qmax	Baseline, 6 weeks, 12 months
To describe urological complications in patients with and without LUTS	Frequency and type of complications	6 weeks and 12 months
To correlate pre-transplant LUTS with graft function	Renal function measures (eGFR, creatinine)	6 weeks, 12 months
Impact of waiting times on outcomes	IPSS/ ICIQ total score and QoL sub-score	12 months post wait listing

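### The composite urological complication outcome has two current definitions that differ in the recurrent-UTI and ureteric-leak items, so some patients are events under one list and non-events under the other

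*Protocol*

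**What the plan says.** The protocol lists the seven components of the 12-month composite twice, in the Scientific Summary (Methods) and in section 3 (Primary outcome measures). Items 1, 4, 5, 6 and 7 agree in substance. Items 2 and 3 do not.

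- **Item 2, Scientific Summary:** "Recurrent culture-proven urinary tract infections (≥ 3 in the first 12 months post-transplant").
- **Item 2, section 3:** "Recurrent culture-proven urinary tract infections (≥ 2 in the first 6 months/ ≥ 3 in the first 12 months post-transplant").
- **Item 3, Scientific Summary:** "Ureteric leak or suspected ureteric leak requiring surgical or radiological intervention".
- **Item 3, section 3:** "Ureteric leak or suspected ureteric leak", where the item ends.

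Item 6 is the same in both lists: "Any patient undergoing any surgical or radiological intervention for a urological complication (excluding routine stent removal post-transplant) within the first 12 months of transplantation". The endpoint table in section 3 summarises the outcome as "Incidence of urological complications (retention, recurrent UTIs, ureteric obstruction, need for CIC, graft pyelonephritis etc as above"). Section 8 (Sample size) says, from the centre's previous two years of data, that "we anticipate that between 50-60% of patients will have one of the composite urological complication outcomes", without saying which list was applied.

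**The concern.** Both lists are current text and neither is given precedence. Two analysts who each follow the protocol could classify the same patient differently and report different complication rates.

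Four uses of the composite are exposed:

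- Section 8 (Data analysis) makes the prevalence of urological complications one of the primary analysis aims.
- Primary objective (b) describes LUTS scores across adverse outcomes.
- The historical-cohort comparison would show a difference created by definition alone if each cohort were counted under a different list.
- The results are meant to inform the sample size and endpoint of a later interventional study.

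If the choice is left until the data are in, the event rate can be chosen with the data in view. There is also a practical risk. The post-transplant study visits in section 7 are at weeks 6 and 52, with none at 6 months. A form built from the Summary might hold only a 12-month UTI count, and the 6-month rule could not then be applied from it.

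**Working it through.** **Step 1. The plan's own figure.** The 50-60% cannot be rebuilt. The centre data are not in the protocol and the figure is not tied to either list.

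**Step 2. UTI item, case by case.** Section 3 separates its two thresholds with a slash, so both readings are shown.

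| UTIs in months 0-6 | UTIs in 12 months | Summary | Section 3, slash = or | Section 3, slash = and |
|---|---|---|---|---|
| 2 | 2 | no | **yes** | no |
| 1 | 2 | no | no | no |
| 2 | 3 | yes | yes | yes |
| 1 | 3 | yes | yes | **no** |
| 0 | 3 | yes | yes | **no** |

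Bold marks disagreement with the Summary. Under 'or', the discordant patients are those with exactly two UTIs, both in months 0-6. Under 'and', the discordance falls on other patients but does not disappear.

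**Step 3. Leak item.** A leak that needs surgical or radiological intervention counts under both lists. A suspected leak without it counts under section 3 only, and item 6 does not recover it because item 6 also requires an intervention. For a confirmed leak without intervention, the answer depends on whether the Summary's qualifier attaches to both kinds of leak (discordant) or to suspected leaks only (concordant).

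With the slash read as 'or', section 3 is therefore the broader list.

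**Step 4. Size of the UTI discordance.** Every input here is an assumption, since the protocol gives no UTI rate. Let N be a patient's UTI count over 12 months, with mean m, and f the share of UTIs falling in months 0-6, each UTI being early independently of the others. Then

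discordant share = P(N = 2) × f².

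For Poisson counts, P(N = 2) = e^(−m) m²/2:

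- m = 0.5, f = 0.50: 0.6065 × 0.125 × 0.25 = 0.019, or 1.9 points.
- m = 1.5, f = 0.65: 0.2231 × 1.125 × 0.4225 = 0.106, or 10.6 points.

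Overdispersed counts (gamma-Poisson, shape 1) with m = 1 give P(N = 2) = 0.5 × 0.5² = 12.5% and P(N ≥ 3) = 0.5³ = 12.5%. With f from 0.50 to 0.65, section 3 adds 12.5% × 0.25 = 3.1 to 12.5% × 0.4225 = 5.3 points. The UTI component rises from 12.5% to between 15.6% and 17.8%.

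Wider Poisson inputs give a wider range:

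- m = 0.25, f = 0.50: 0.7788 × 0.03125 × 0.25 = 0.006, or 0.6 points.
- m = 1.5, f = 0.70: 0.2231 × 1.125 × 0.49 = 0.123, or 12.3 points.

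**Step 5. Scale.** The 95% half-width for a proportion is 1.96 × √(p(1−p)/n). For p = 0.5 to 0.6 it is 9.8 to 9.6 points at n = 100, the target for each part of the study. It is 11.0 to 10.7 points at n = 80, the 40 men plus 40 women whom section 8 expects to have complete data. The top of the assumed UTI range is about as large as the sampling error; the bottom is well inside it.

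**The case against.** The study is exploratory, with no stated alpha, power or effect size, and section 8 does not list the 50-60% among the three factors behind the sample size. It says the broad definition was deliberate and can be refined later. Relating LUTS severity to complications is optional under Data analysis, and the endpoint table also reports complications by type. All of this stands and limits the consequence. It does not remove the conflict, because complication prevalence is itself a primary analysis aim.

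The size is also open to challenge. It rests on assumed rates and concerns one component. Some discordant patients will meet another item; if half did (an assumption), 1.9 to 10.6 points would become about 1 to 5. Discordant leaks cannot be quantified at all.

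A reader might infer more than the protocol supports:

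- **That the endpoint table is a third definition.** It names ureteric obstruction, which neither list does, and mentions graft pyelonephritis without the condition in "Sepsis of urinary source requiring hospital admission (including graft pyelonephritis"). But the cell is shorthand that refers back to the list above it, and obstruction can already count through item 4 or item 6. It needs tidying only.
- **That every prediction objective depends on the composite.** Graft outcomes are measured by eGFR and creatinine, and change in LUTS by symptom scores and flow measures. Neither uses it.
- **That the Summary's leak item is redundant given item 6.** This holds only if the qualifier covers confirmed as well as suspected leaks. Overlap between components is in any case no contradiction.
- **That section 3 counts untreated leaks.** It omits the surgical or radiological condition and says nothing about conservative treatment.

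**Conclusion.** The inconsistency is established from the text: two current sections define one primary outcome differently in items 2 and 3. With the slash read as 'or', a patient whose only event is exactly two UTIs, both in the first 6 months, or a suspected leak without surgical or radiological intervention, is classified in opposite ways.

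Under assumed rates of 0.5 to 1.5 UTIs per patient-year with 50 to 65% early, the UTI component shifts by about 2 to 11 points, and by less at lower rates. That is a ceiling on what the UTI item can add to the composite and should not be read as an estimate of the change in the composite.

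One might also infer that the sample size is undermined. It is not: it rests on feasibility, description of the score distribution and the existing literature, so no sample size or power figure changes. What is left ambiguous is the complication prevalence, the outcome in objective (b), the historical-cohort comparison, the meaning of the 50-60%, and the event rate carried into a later trial. This should be corrected before data collection.

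**What to change.** Reconcile the Scientific Summary and section 3 to one list and use it everywhere. Section 3 is the natural default: it is the outcome-measures section, and it fits the breadth that section 8 says was intended. The choice belongs to the investigators. Within the adopted list:

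- Replace the slash in item 2 with 'or', if that is what is meant.
- State whether the intervention qualifier in item 3 applies to confirmed leaks, suspected leaks, both or neither.
- Record the date of each culture-proven UTI, so that a 6-month rule can be applied.
- Align the endpoint table with the list, including its mention of ureteric obstruction.
- Apply the same definition to the historical cohort.
- State which definition the 50-60% refers to, and re-count the centre's data if it used the other one.

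The cost is protocol wording, a date field on the collection form and at most one re-count of existing data. The anticipated rate may move; recruitment targets do not.
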